8.2 Potential Benefits

Subjects may not receive any benefit from this study. However, there is the potential that the nutrition counseling and diet support received may result in reductions in weight and/or improvements in insulin sensitivity, visceral adipose tissue, hepatitis steatosis, and adipose-tissue associated inflammation, potentially reducing cardiovascular disease risk.

9 Research Use of Stored Human Samples, Specimens or Data

- Intended Use: Samples and data collected under this protocol may be used to study HIV, immune disorders, metabolic disorders, and inflammation. Limited genetic testing will be performed.
- Storage: Access to stored samples will be limited using a locked room or locked freezer. Samples and data will be stored using codes assigned by the investigators. Data will be kept in password-protected computers. Only investigators will have access to the samples and data.
- Tracking: Samples and data acquired as part of this protocol will be tracked using the Clinical Research Information Management System of the NIAID (CRIMSON) database.
- Disposition at the Completion of the Protocol: In the future, other
 investigators (both at NIH and outside) may wish to use these samples and/or
 data for research purposes. If the planned research falls within the category of
 "human subjects research" on the part of the NIH researchers, IRB review and
 approval will be obtained. This includes the NIH researchers sending out coded

and linked samples or data and getting results that they can link back to their subjects.

• Reporting the Loss or Destruction of Samples/Specimens/Data to the IRB:

Any loss or unanticipated destruction of samples (for example, due to freezer malfunction) or data (for example, misplacing a printout of data with identifiers) that meets the definition of a reportable event will be reported to the NIH IRB according to Human Research Protections Program (HRPP) Policy 801. Additionally, subjects may decide to withdraw from research participation at any point and not have their samples stored. In this case, the PI will destroy all known remaining samples and report what was done to both the subject and to the IRB. This decision will not affect the subject's participation in other protocols at NIH.

10 Remuneration Plan for Subjects

Eligible subjects will receive partial remuneration from the NIH for immediate costs associated with study-related expenses (eg, transportation and lodging) according to established NIH/NIAID guidelines. Subjects will also be compensated for the time and inconvenience of study participation according to the attached schedule (see Appendix A). Thus, remuneration up to \$880 for completion of the entire study, commensurate with the time and inconvenience of study participation including blood draws, imaging, inpatient assessments, and optional adipose tissue biopsies.

11 Assessment of Safety

11.1 Toxicity Scale

The investigator will assess all AEs with respect to **Seriousness** (criteria referenced in Section 11.3 Definitions), **Severity** (intensity or grade) and **Causality** (relationship to study interventions according to the following guidelines

Severity: The Investigator will grade the severity of each AE according to the "Division of AIDS (DAIDS) Table for Grading the Severity of Adult and Pediatric Adverse Events" Version 2.1, July 2017, which can be found at:

https://rsc.tech-res.com/docs/default-source/safety/division-of-aids-(daids)-table-for-grading-the-severity-of-adult-and-pediatric-adverse-events-corrected-v-2-1.pdf

Some grade 1 lab parameters on the DAIDS Toxicity Table (fibrinogen, potassium [low], uric acid [males only, elevated]) fall within the NIH lab reference range for normal values. These normal values will not be recorded as grade 1 AEs. The grade 1 values for these tests will be recorded as follows:

• Fibrinogen: 100-176 mg/dL

Potassium (low): 3.0-3.3 mmol/L

Uric acid (males): 8.7-10.0 mg/dL

• Magnesium (low): 0.60-0.65 mmol/L

Causality: Causality (likelihood that the event is caused by the study intervention will be assessed considering the factors listed under the following categories:

Definitely Related:

- reasonable temporal relationship
- follows a known response pattern
- clear evidence to suggest a causal relationship
- there is no alternative etiology

Probably Related:

- reasonable temporal relationship
- follows a suspected response pattern (based on similar agents)
- no evidence of a more likely alternative etiology

Possibly Related

- reasonable temporal relationship
- little evidence for a more likely alternative etiology

Unlikely Related

- does not have a reasonable temporal relationship or
- good evidence for a more likely alternative etiology

Not related

- does not have a temporal relationship
- definitely due to an alternative etiology

Other factors will also be considered for each causality category when appropriate. Causality assessment is based on available information at the time of the assessment of the AE. The investigator may revise the causality assessment as additional information becomes available.

11.2 Recording/Documentation

At each contact with the subject, information regarding AEs will be elicited by appropriate questioning and examinations. All events, both expected/unexpected and related/unrelated will be recorded on a source document. Source documents will include progress notes, laboratory reports, consult notes, phone call summaries, survey tools and data collection tools. Source documents will be reviewed in a timely manner by the research team. All reportable AEs that are identified will be recorded in CRIMSON. The start date, the stop date, the severity of each reportable event, and investigator judgment of the relationship and expectedness to the study intervention(s) will also be recorded in CRIMSON.

11.3 Definitions

Reportable events and adverse events are defined in NIH HRPP Policy 801.

11.4 Reporting Procedures

Unanticipated problems (UPs), non-compliance, and other reportable events will be reported to the NIH IRB according to Policy 801.

The principal investigator will report UPs, major protocol deviations, and deaths to the NIAID clinical director according to institutional timelines.

11.5 Reporting of Pregnancy

In the event of pregnancy:

- The subject will discontinue the study intervention (caloric restriction) and procedures but continue to follow-up in person and/or over the phone for safety and outcome
- Pregnancy will be reported to the IRB
- Research subject will be advised to notify the obstetrician of her study participation

11.6 Type and Duration of the Follow-up of Subjects after AEs

AEs that occur from the time of enrollment of the subject are followed until the final outcome is known or until the end of the study follow-up period. SAEs that have not resolved by the end of the follow-up period are followed until final outcome is known. If it is not possible to obtain a final outcome for an SAE (eg, the subject is lost to follow-up), then the reason a final outcome could not be obtained will be recorded by the investigator.

11.7 Withdrawal of an Individual Subject

An individual subject will be withdrawn for any of the following:

- An individual subject's decision (the investigator will attempt to determine the reason for the subject's decision.)
- Non-compliance with study procedures to the extent that it is potentially harmful to the subject or to the integrity of the study data.
- Any clinical AE, laboratory abnormality, intercurrent illness, other medical condition or situation occurs such that continued participation in the study would not be in the best interest of the subject.
- The subject loses the capacity to provide ongoing informed consent.
- Development of an exclusion criteria may be cause for discontinuation.

11.8 Replacement of a Subject Who Discontinues Study Treatment

If a subject withdraws after fewer than 12 weeks on study diet assignment, then they will be replaced. If a subject is replaced, their data will still be included for the safety assessments.

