We propose to study the benefits of a 2-5 ICR strategy on weight, insulin resistance, and cardiovascular disease markers in obese HIV-infected adults with features of the metabolic syndrome. In a prospective pilot study, 50 HIV-infected adults will be randomized 1:1 to ICR or standard-of-care instruction of healthy diet and lifestyle for a 12-week intervention period. We hypothesize that ICR (2 days per week) will be an effective and acceptable diet strategy that will result in significant weight reduction, improvements in insulin sensitivity, and related metabolic parameters.

1 Background Information and Scientific Rationale

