2.2 Secondary Objectives

- To evaluate the effects of ICR on body composition, including visceral adiposity and hepatic steatosis, lipids levels, metabolic biomarkers, biomarkers of inflammation and immune activation, and mood.
- To assess the tolerability of ICR.

3 Study Design

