3.1.1.2 Secondary Endpoints

- 1. Tolerance and adherence to diet assignment
- 2. Change in the following after 12 weeks of caloric restriction:
 - Visceral adiposity as measured by dual x-ray absorptiometry (DXA) and waist circumference
 - Fat and lean mass as measured by DXA
 - Hepatic steatosis and liver stiffness as measured by transient elastography
 - Lipid profile
 - REE as measured by indirect calorimetry
 - Serum biomarkers of inflammation (eg, CRP, TNF-alpha) and immune activation

4 Study Population

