6.6 Early Termination Visit

If a subject's participation is terminated before completing the study, then they will be asked to return to the NIH Clinical Center for a Termination Visit. Laboratory tests and study evaluations to be conducted at that visit will be determined on the basis of the subject's health, their willingness, and the appropriateness of the test at that time point.

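### Early leavers are replaced and given a stated use only in the safety assessments, so adherence to and persistence on the fasting diet may be overstated

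*Combined protocol and SAP*

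**What the plan says.** Section 2.2 sets a secondary objective: "To assess the tolerability of ICR". The first secondary endpoint in 3.1.1.2 is "Tolerance and adherence to diet assignment", and the Précis hypothesises that "ICR (2 days per week) will be an effective and acceptable diet strategy". Acceptability is thus part of what the study sets out to show.

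Section 11.8 has two sentences. The first is "If a subject withdraws after fewer than 12 weeks on study diet assignment, then they will be replaced"; the second is "If a subject is replaced, their data will still be included for the safety assessments".

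Section 11.7 lists the grounds for withdrawal. They include the subject's own decision, in which case "the investigator will attempt to determine the reason for" it, and also "Non-compliance with study procedures to the extent that it is potentially harmful to the subject or to the integrity of the study data". For the early termination visit, section 6.6 says: "Laboratory tests and study evaluations to be conducted at that visit will be determined on the basis of the subject's health, their willingness", together with whether a test is appropriate at that time.

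Section 12.4 defines one analysis set, for the primary endpoint: randomised subjects with both a baseline and a week 12 assessment, however well they complied. Its paragraph on secondary endpoints describes t-tests of change, names no population, and mentions neither tolerance nor adherence.

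**The concern.** For most endpoints a subject who leaves early is a missing value. For adherence and persistence, leaving because the diet could not be followed is the result itself. A rule that exchanges that subject for a new one, and names no use for the departed subject's data outside safety, can take failures out of the numerator and the denominator together.

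If the adherence summary then follows the only analysis set in the plan, it describes people who reached week 12. A diet that a sizeable minority gave up could be reported as well followed. Readers planning a larger trial would take from this pilot too favourable a view of how many people can keep to ICR.

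**Working it through.** **What the passages give together.** Replacement applies to any withdrawal before 12 weeks, for any reason and in either arm (11.8). Safety is the only use named for the replaced subjects' data (11.8). The only defined set is completers (12.4). The endpoint has no set of its own (3.1.1.2, 12.4). So no passage places an early leaver in the adherence summary, and none expressly shuts one out.

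**The plan's own figures.** The documents give no figure for tolerance or adherence. The relevant one is the dropout scenario in 12.3, 17 remaining of 25 per arm: 1 − 17/25 = 32%, described there as about 30%. The power stated for that scenario reproduces: difference 4 kg, SD 3.24, 17 per arm, two-sided 0.05, noncentral t gives 93.69% against 93.7%. (The 96.7% stated for 25 per arm does not; the same method gives 98.97%. Nothing here depends on it.)

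**Persistence.** Among those first randomised: 17/25 = 68%. In an arm refilled until 25 have completed: 25/25 = 100%. At 32% dropout, 25 completers need 25/0.68 = 36.8, so 37 randomised and 12 leavers per arm. Two arms need 74, within the accrual ceiling of 100 in the Protocol Summary.

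**Adherence.** Measure: mean share of restricted days achieved in the ICR arm. Planned days: 2 × 12 = 24.

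- a = adherence among completers; assumed, 80% or 85%
- d = dropout; 32%, from 12.3
- s = share of withdrawals that are diet-related; unknown, 0 to 1
- w = weeks on diet credited before stopping; assumed, 0 or 4 of 12
- leavers for other reasons are assumed to adhere as completers do

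All-randomised adherence = a × [1 − d × s × (1 − w/12)], so the completer figure overstates by a × d × s × (1 − w/12).

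| a | w | s = 0 | s = 0.5 | s = 1 |
|---|---|---|---|---|
| 80% | 0 | 0 | 12.8 points | 25.6 points |
| 80% | 4 | 0 | 8.5 points | 17.1 points |
| 85% | 0 | 0 | 13.6 points | 27.2 points |
| 85% | 4 | 0 | 9.1 points | 18.1 points |

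Direct check of the last cell: (17 × 0.85 + 8 × 0.85 × 4/12)/25 = (14.45 + 2.27)/25 = 66.9%, and 85 − 66.9 = 18.1 points.

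**The case against.** A reader might infer more: that replaced subjects are kept for safety and nothing else, that the endpoint is measured in those who stayed, and that acceptability will be overstated. The documents do not support this.

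- Section 11.8 does not contain the word only. It is a statement about keeping data. It reads naturally as an exception to exclusion elsewhere, but that is a reading.
- The completer set in 12.4 is stated for the primary endpoint. For tolerance and adherence the population is unspecified.
- Much of tolerance may already count as safety. Section 6.4 describes the visits at weeks 1, 4, 8 and 12 as safety visits and gives the Symptoms Review Questionnaire at them; 8.1 treats low energy, feeling cold and irritability as adverse events; 11.2 lists survey tools among the source documents. Symptom data up to withdrawal would then be retained.
- Section 11.7 does not remove poor adherers in general, only those whose non-compliance could harm the subject or the data. Someone who abandons the restricted days but attends week 12 stays in the completer set.
- Diaries are reviewed at visits (5.1), and a reason is sought when the subject chooses to leave, so information before withdrawal exists.
- The 17 per arm is a power scenario covering all reasons and both arms, not a forecast of diet failure.

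All of this stands, and it limits the point to one of risk. It does not remove it. Adherence and persistence are not safety measures in the ordinary sense, and collecting diaries does not settle whose diaries are summarised. Section 6.6 requires no particular assessment at termination, so a subject who stops between visits may leave no record close to stopping.

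**Conclusion.** The point holds as a risk created by a stated rule, not as a demonstrated bias. The replacement and retention rule in 11.8, the completer set in 12.4 and an endpoint without a population leave early leavers with no stated place in the adherence part of the first-listed secondary endpoint. Any resulting error would favour ICR.

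Its size depends mainly on how many withdrawals are diet-related, which the documents cannot tell us. The lower end of the range is zero. The upper end of about 17 to 27 points assumes that every withdrawal is diet-related, that completers achieve 80 to 85% of restricted days, and that dropout reaches 32%; it would shrink with lower dropout. The contrast of 68% with about 100% for persistence further assumes that persistence is reported in the refilled set, which the plan neither says nor rules out.

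The change is worth making because it is cheap and concerns a named objective.

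**What to change.** - **Section 11.8:** state that data from replaced subjects are included in the safety assessments and in the tolerance and adherence endpoint.
- **Sections 3.1.1.2 and 12.4:** define the endpoint in all randomised subjects. By arm, report the proportion still on the assigned diet at week 12, with time and reason for stopping. In the ICR arm only, since the standard-of-care arm has no restricted days, report restricted days achieved out of the 24 planned. Count zero after withdrawal for diet-related reasons, with a sensitivity analysis for how other withdrawals are handled.
- **Section 6.6:** request the Symptoms Review Questionnaire, the diary and the reason for stopping at termination, by telephone if needed and where the subject is willing.

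The cost is wording in four sections. The instruments are already in the schedule, and neither the diet, the withdrawal rules nor the primary tests change. The downside is that the reported tolerability and adherence figures may be less favourable.

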11.9 Safety Monitoring Plan

The data gathered during this study will be monitored by the PI for safety and compliance with protocol-specified requirements. Subjects will be closely monitored for weight loss. If a subject loses ≥5% of their body weight within a 2-week period, additional safety visits will be scheduled to monitor body weight more closely. If weight loss in that range or greater continues to occur, subjects will be asked to discontinue caloric restriction and monitored.

12 Statistical Considerations

12.1 Overview and Design

This is a randomized controlled, study of 12 weeks of ICR versus standard of care. Changes from baseline to 12 weeks in measures of the primary endpoints (weight and insulin sensitivity) and secondary endpoints (eg, hepatic fat content, inflammatory biomarkers) will be compared between the 2 study arms. The 12-week follow-up period after the randomized portion of the study is designed to monitor changes in weight and metabolic parameters after completion of the 2-5 ICR diet arm and the standard-of-care arm.

12.2 Study Hypotheses

Subjects in the 2-5 ICR group will experience greater weight loss and greater improvements in insulin sensitivity and related metabolic parameters, including decreased visceral adipose tissue and hepatic fat content, compared to subjects in the standard of care arm.

12.3 Sample Size Justification

Using an alternate day fasting strategy for weight loss in obese adults (n=13), Catenacci et al [57] observed that subjects lost 8.2±0.9 kg (mean ± standard error of the mean) after 8 weeks. For sample size justification, we will use a conservative estimate of 8-kg weight loss after 12 weeks with ICR, and assume 4-kg weight loss among the observation group due to monitoring and counselling through study visits. Therefore, using the standard deviation estimate from Catenacci et al. of 3.24, we will have 96.7% power to detect a 4-kg difference in weight loss between treatment arms with 25 subjects in each arm. With 17 subjects per arm (ie, approximately a 30% dropout rate), the power will be 93.7% to detect a 4-kg difference in weight loss.

In previous studies of ICR, HOMA-IR improvements ranged from 9% to 30%, depending on a number of factors, including the duration of the study, extent and timing of caloric restriction, and whether or not meals were provided [59]. Assuming a baseline HOMA-IR of 1.5, a standard deviation of change in HOMA-IR of 0.25, a study size of

25 subjects per arm, we will have >80% power to detect the difference between a 25% improvement in insulin sensitivity with ICR versus a 10% improvement in the observation arm as measured by HOMA-IR. The power to detect this difference will be 72.1% with 17 subjects per arm.

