12.4 Description of the Analyses

For the primary endpoint, the between group effect on weight will be tested using a two-sided t-test (p-value <0.05) of the calculated change in weight from baseline to 12 weeks. This will be conducted using on-treatment data, ie, data from all randomized subjects who completed baseline and 12 weeks evaluations regardless of reported compliance. Similarly, between group differences in insulin resistance measured by HOMA-IR will be determined. A secondary analysis will use analysis of covariance to adjust for the baseline value of the given endpoint.

In the analyses of the secondary endpoints (eg, visceral adiposity, serum lipids, markers of inflammation, hepatic fat content results), two-sided t-test comparing change from baseline to 12 weeks will be calculated between groups. In addition, within group paired t-tests may be performed to determine if, during the 12 week follow up if any of the changes during the randomized intervention portion of the study are sustained after 12 weeks of no intervention.

13 Ethics/Protection of Human Subjects

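### The stated 96.7% power for weight at 25 per arm does not follow from the plan's own inputs, which give 99.0%

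*Combined protocol and SAP*

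**What the plan says.** Section 12.3 (Sample Size Justification) bases the weight calculation on a cited alternate-day fasting pilot with 13 subjects and a mean loss of 8.2 kg (standard error 0.9 kg). For the fasting arm, "we will use a conservative estimate of 8-kg weight loss after 12 weeks with ICR". For the comparison arm the authors "assume 4-kg weight loss among the observation group due to monitoring and counselling through study visits". That leaves a difference of 4 kg. The SD is given as 3.24 kg.

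Two power figures for weight follow. At full enrolment, "we will have 96.7% power to detect a 4-kg difference in weight loss between treatment arms with 25 subjects in each arm". At 17 per arm, described as roughly 30% dropout, "the power will be 93.7% to detect a 4-kg difference in weight loss".

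For HOMA-IR the section claims more than 80% power at 25 per arm, and then: "The power to detect this difference will be 72.1% with 17 subjects per arm".

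Section 12.4 (Description of the Analyses) fixes the test. The effect on weight is to be "tested using a two-sided t-test (p-value <0.05) of the calculated change in weight". Section 3.1 gives 1:1 randomization. Neither 12.3 nor 12.4 mentions a split of alpha between the two primary measures or any inflation of the variance.

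**The concern.** Every input needed to recompute the weight power is printed, and the result at 25 per arm is not the one the plan gives. This is the headline power for a primary endpoint, in the section that justifies the sample size. A reader who cannot reproduce it cannot tell whether the N, the SD, the difference or alpha was misreported.

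The error also affects the one comparison the paragraph offers, between full enrolment and about 30% dropout. As printed, dropout costs 3.0 points of power (96.7% to 93.7%). From the stated inputs it costs 5.3 points (98.97% to 93.69%).

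**Working it through.** **Inputs**

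- Difference in mean weight change: 8 − 4 = 4 kg (section 12.3).
- SD of weight change: 3.24 kg (section 12.3). This agrees with the quoted standard error: 0.9 × √13 = 3.245.
- Test: two-sided t-test at 0.05 (section 12.4).
- Allocation: 1:1 (section 3.1), with n = 25 or 17 per arm (section 12.3).

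**Formula.** For a two-sample, equal-variance t-test with n per arm, the degrees of freedom are 2n − 2 and the noncentrality is λ = Δ / (SD × √(2/n)). Power is the probability that a noncentral t variable with these parameters falls outside ± the two-sided 5% critical value.

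**Step 1: reproduce the plan's figures at 17 per arm**

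- Weight: λ = 4 / (3.24 × √(2/17)) = 3.60, df 32, critical value 2.037. Power is 93.69%; the plan prints 93.7%.
- HOMA-IR: the difference is 1.5 × (0.25 − 0.10) = 0.225, with SD 0.25. λ = 0.225 / (0.25 × √(2/17)) = 2.62. Power is 72.06%; the plan prints 72.1%.

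Both agree to the printed decimal, which confirms the test, its sidedness, alpha and the SD.

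**Step 2: the same calculation at 25 per arm**

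- HOMA-IR: λ = 3.18, power 87.65%. The plan's claim of more than 80% is true.
- Weight: λ = 4 / (3.24 × √(2/25)) = 4.36, df 48, critical value 2.011. Power is **98.97%**; the plan prints 96.7%.

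Rounding of the SD does not explain the gap: 3.245 gives 98.95%. A normal approximation moves further away, to 99.2%.

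**Step 3: could one unstated input explain 96.7%?** Each of the first three rows solves for 96.7% at 25 per arm and then recomputes power at 17 per arm. The fourth tests an equal split of alpha between the two primary measures.

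| Input changed | Value | Power at 25 per arm | Power at 17 per arm (printed: 93.7%) |
|---|---|---|---|
| SD | 3.65 kg | 96.7% | 87.3% |
| Difference | 3.55 kg | 96.7% | 87.3% |
| Two-sided alpha | 0.017 | 96.7% | 85.1% |
| Two-sided alpha, halved | 0.025 | 97.8% | 88.8% |

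None of these yields both printed weight figures.

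**Step 4: where 96.7% does occur.** With the stated inputs, power at 20 per arm is 96.74%. The plan describes no 20-per-arm scenario, so a carry-over from one is only an inference. Unequal arms of 25 and 17 give 96.9%, which is not the printed value, and the text specifies 25 in each arm.

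**The case against.** The arithmetic is hard to contest; the case on the other side is about how much it matters and how far the conclusion reaches.

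- **Nothing turns on it.** The printed power is too low, so the design is better powered for weight than claimed. This stands, and it is why the point is minor.
- **The SD is far less certain than the correction is large.** It rests on 13 subjects. Assuming normal data, a 95% chi-square interval for it is about 2.32 to 5.35 kg, and power at 25 per arm over that range runs from above 99.9% down to about 74%. This also stands: 99.0% is what the plan's inputs give, not a better forecast of the trial's real power.
- **The dropout contrast is not a separate fault.** It follows from the same wrong number, and the power remaining at 17 per arm is printed correctly. Section 11.8 also provides for replacing subjects who withdraw before 12 weeks, and the accrual ceiling is 100 against a sample size of 50, so 17 per arm may not be the expected outcome. This is fair, but it changes neither printed figure.
- **Changing one input at a time does not exclude every combination.** Strictly true: an SD near 7 kg with a two-sided alpha near 0.76 comes close to both weight figures. But section 12.4 fixes alpha at 0.05 and section 12.3 fixes the SD at 3.24 kg, so no plausible single set of inputs gives both.
- **Reproducing the HOMA-IR figures does not validate their inputs.** Agreed. The check shows only that those statements follow from the assumed baseline of 1.5 and SD of 0.25.

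**Conclusion.** The concern holds. Under the plan's own difference, SD, test and alpha, with equal arms of 25, power for weight is 99.0%, not 96.7%. That is an understatement of 2.3 points: the type II error is 1.0% rather than 3.3%. The 93.7% and 72.1% figures at 17 per arm and the HOMA-IR claim of more than 80% at 25 per arm are arithmetically correct.

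The conclusion needs no assumption beyond the printed inputs and a standard equal-variance t-test, which the plan's own 17-per-arm figures confirm. The error is minor and conservative, and the sample size, test and endpoint are unaffected.

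**What to change.** In section 12.3, change 96.7% to 99.0% for 25 per arm and leave 93.7% for 17 per arm. If 96.7% was meant for a different number per arm, state that number. If it came from a different SD, difference or alpha, state that input and recompute the 17-per-arm weight figure as well, because 93.7% would no longer hold. The HOMA-IR power statements need no arithmetic correction.

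The cost is one number in one sentence.
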